### 6.3 Duration of Treatment

This is a single dose study.

## **6.4 Removal from Study Treatment and off-Study Criteria**

Participation in this research study is completely voluntary. Subjects are free to withdraw from this study at any time by informing the investigator. If a subject, for whatever reason, no longer appropriate to continue receiving study therapy, they will be notified and withdrawn from the study. Furthermore, if the subject is non-compliant (e.g. non-compliant with visits, concomitant medications.) they will be withdrawn from the study and a replacement subject may be recruited.

Additionally, prior to removal from study, effort must be made to have all subjects complete a safety visit approximately 30 days following the last dose of study therapy.

### **6.4.1 Criteria for Removal from Study Treatment**

- Completion of protocol therapy
- Participant requests to be withdrawn from the study
- Investigator discretion
- Lost to follow-up or noncompliance
- AEs or safety concerns by Investigator or Sponsor
- Positive alcohol test, cotinine test, or drug screen
- Positive pregnancy test.

### **6.4.2 Off-Study Criteria**

Once a subject is taken off study, no further data can be collected.

- Participant request to be withdrawn from study
- Subject withdrawal from the follow-up period
- Subject completed all protocol required follow-ups
- Death
- Screen failure

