#### **4.2.3 Subject Stopping Criteria:**

Dosing will be permanently stopped for any individual subject experiencing any of the following:

- Any SAE, regardless of causality to the study drug.

- Subject experience DLT.
- Hypersensitivity or anaphylactic reaction following start of infusion.
- Medical condition that is judged by the Investigator as to jeopardize the subject's safety if he or she continues to receive the study drug.
- QTc prolongation defined as QTcF increasing  $\geq 60$  msec and persisting for at least 10 minutes or QTcF  $> 500$  msec and persisting for at least 30 minutes, or episode of torsade de pointes.

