### **11.5 Tabulation of Individual Participation Data**

Data tabulations will summarize the following numbers of subjects:

- Enrolled
- Study drug treatment dose received
- Evaluable for safety
- Protocol violations
- Protocol completions
- Withdraw from study due to:
  - Adverse event
  - Physician's recommendation
  - Withdrew consent
  - Lost to Follow-up
  - Other reasons as collected on the eCRF

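### Sections 6.4 and 6.4.2, read literally, end data collection for dosed subjects whose therapy is stopped or who are non-compliant, against the plan's own follow-up rules

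*Combined protocol and SAP*

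**What the plan says.** Section 6.4 gives two mandatory routes out of the study. The first concerns a subject who is, "for whatever reason, no longer appropriate to continue receiving study therapy, they will be notified and withdrawn from the study". The second concerns a non-compliant subject, with visits and concomitant medications as the examples: "they will be withdrawn from the study and a replacement subject may be recruited". The next paragraph asks that, before removal from study, "effort must be made to have all subjects complete a safety visit approximately 30 days following the last dose of study therapy".

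Section 6.4.1 lists reasons for removal from study treatment. Among them are "Completion of protocol therapy", "Lost to follow-up or noncompliance", and adverse events or safety concerns. Section 6.4.2 covers subjects who are off study. It opens with "Once a subject is taken off study, no further data can be collected" and then lists the subject's own request, withdrawal from follow-up, completion of follow-up, death and screen failure.

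The follow-up rules stand elsewhere:
- Section 7.1 requires AE follow-up to the later of 30 days after dosing and resolution of drug-related toxicity.
- Section 10.1 requires every AE to be followed to baseline or stabilization.
- Section 10.4 collects SAEs through 30 days after dosing and follows them to resolution or stabilization, or until this is no longer possible. It makes related SAEs reportable without time limit.

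Section 4.2.3 states: "Dosing will be permanently stopped for any individual subject experiencing any of the following". Its list includes any SAE, a DLT, and hypersensitivity after the infusion has begun. Section 6.3 confirms that one dose is given.

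**The concern.** Sections 6.4 and 6.4.2 together turn the end of treatment, or a compliance failure, into the end of observation. In a single-dose trial, taking a dosed subject out of the study spares no further exposure. It only stops data from being collected.

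Subjects whose infusion is stopped under section 4.2.3 matter most. They bear directly on the primary safety endpoint, and on a literal reading section 6.4 withdraws them. They stay in the safety population (section 11.3.2), but their later safety data would be truncated, and section 11.4.2 plans no imputation. A withdrawal inside the 7-day DLT window would also shorten the week-1 data that the SRC reviews before escalation (sections 4.2.2 and 10.9).

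**Working it through.** The main check is a comparison of texts. The only arithmetic is a count of scheduled samples.

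**1. Does the data bar conflict with the safety follow-up rules?** Take a subject whose infusion is stopped for a DLT or hypersensitivity.
- Section 4.2.3 ends dosing.
- Section 6.4 withdraws from the study anyone for whom therapy is no longer appropriate, whatever the reason.
- Section 6.4.2 then bars further data and states no safety exception.
- Sections 7.1, 10.1 and 10.4 require follow-up of the same subject to continue.

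These cannot all be followed. The exit in section 10.4, where follow-up is no longer possible, can cover a lost subject. It does not naturally cover a withdrawal that the protocol itself imposes. Sections 7.1 and 10.1 have no such exit.

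**2. Does section 6.4 agree with the plan's own two lists?**

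| Reason | 6.4 | 6.4.1 (off treatment) | 6.4.2 (off study) |
|---|---|---|---|
| Noncompliance | withdrawn from study | listed | not listed |
| AE or safety concern | withdrawn, if therapy is no longer appropriate | listed | not listed |
| Therapy completed | not addressed | listed | not listed |

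The last row settles how the lists relate. Every fully dosed subject completes therapy on Day 1, yet follow-up runs to Day 30 (section 4.2). Removal from treatment therefore cannot by itself mean off study, but section 6.4 treats it so in the first two rows.

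**3. Does the safety visit at about 30 days repair this?** In part. It is one visit, it is best effort, and it is described as a safety visit. It does not provide the interim PK and ADA samples, and it does not cover follow-up to resolution beyond Day 30.

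**4. What could one subject lose?** This is an illustration for a subject treated as off study after Day 2.
- PK times (section 7.2; Table 1 footnote 13): pre-dose, 0.5 h, EOI, then 0.5 h, 4 h, 12 h, 24 h (D2), 48 h (D3), D5, D8, D15, D22 and D30, which is 13. Taken through D2: 7. Lost: 13 − 7 = 6.
- Post-dose ADA draws (section 7.3; footnote 15): D8, D15, D22 and D30, which is 4. Lost: 4 of 4. The Table 1 row appears to carry a further mark at D5; if it counts, the loss is 5 of 5.
- If the 30-day visit took place and its scheduled samples were drawn, the PK loss would be 6 − 1 = 5 of 13, and the ADA loss 3 of 4 (or 4 of 5). Section 6.4 does not say that they would be drawn.

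Samples around the end of infusion are kept in every case, so the loss falls on the later part of the PK profile and on ADA.

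**The case against.** The strongest defence is about timing. Section 6.4 asks for the 30-day visit before removal and for all subjects, so a withdrawn subject may not be off study until about Day 30, and the bar would not bite on Day 2. The bar also stands above a list that omits noncompliance, AEs and stopped infusion. Section 10.4 expressly covers SAEs within 30 days of stopping treatment, and section 4.2.3 stops dosing without saying that the subject leaves the study. A sensible site could read all this together and keep the subject in follow-up.

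Much of that stands. It shows that a benign reading exists and is probably what was intended. It does not show that the text selects it: section 6.4 still says withdrawn from the study, in mandatory terms. Even on the timing reading, the only thing promised is effort toward one safety visit.

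The defence also notes that a stopped infusion needs an event within about 2 hours (section 6.2.4), and that section 6.4.3 allows replacement. Both are fair. Replacement restores the cohort count, however, and not the observation of the subject who had the reaction.

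A reader might infer more than the documents support:
- **A third rule in section 11.5.** The heading "Withdraw from study due to" introduces reasons such as an adverse event or a physician's recommendation. These are tabulation categories. A subject may leave follow-up at their own request with an adverse event as the recorded reason.
- **Study withdrawal for a positive alcohol or cotinine test.** Section 6.4.1 lists such tests separately from noncompliance, under removal from treatment. Section 6.4 does not name them among its examples.
- **Study withdrawal for any concomitant medication.** Section 5.6 allows drugs to manage an AE and judges most other use case by case.
- **A measurable bias in ADA incidence.** Section 11.4.3 does not say how an untested subject is counted, so no size can be derived.

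**Conclusion.** The contradiction is real on the current text and should be corrected. Section 6.4, followed by the bar in 6.4.2, conflicts with sections 7.1, 10.1 and 10.4 and with the division between 6.4.1 and 6.4.2.

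Its size in this trial is unknown, because the documents project no withdrawals. The loss of 6 of 13 PK samples and of every post-dose ADA draw describes one subject under the literal reading with off-study status after Day 2. It is not a forecast. Related SAEs remain reportable under section 10.4, and a site that follows 6.4.1 and 6.4.2 alone would lose little. The documents therefore do not support a claim that safety follow-up after a stopped infusion is absent from the plan, only that the plan gives conflicting instructions about it.

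**What to change.** Reconcile sections 6.4 to 6.4.2 with sections 7.1, 10.1 and 10.4:
- Reword section 6.4 so that removal from study treatment, or noncompliance, does not by itself take a dosed subject off study. A dosed subject who has not withdrawn consent stays in the scheduled safety, PK and ADA follow-up to Day 30, and in AE and SAE follow-up for as long as sections 7.1, 10.1 and 10.4 require.
- State in section 6.4.2 that the data bar applies only to the events listed there, with related-SAE reporting under section 10.4 as a named exception.
- Leave the criteria in sections 4.2.3 and 6.4.1 as they are. This point concerns what happens to observation after a criterion is met, not the criteria.

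The cost is protocol wording; the visits and samples are already scheduled. Some non-compliant subjects will still miss visits, and the rewording cannot recover those data.

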### **6.4.3 Subject Replacement**

Subjects who do not receive the full dose of study drug, or who withdraw from the study or with significant protocol violations may be replaced at the discretion of the investigator after informing the Sponsor.

## 7 STUDY ASSESSMENT AND EVALUATIONS

### 7.1 Description of Assessment Procedures

Below are additional descriptions of study assessments not detailed in [Table 1](#).

**Recording of AEs:** AEs should be documented and recorded per Guidance for Industry *Toxicity Grading Scale for Healthy Adult and Adolescent Volunteers Enrolled in Preventive Vaccine Clinical Trials*. After signing ICF and before the administration, only SAEs related to study intervention will be recorded. All AEs will be recorded once dosing starts and subjects must be followed for AEs for 30 days after the administration, or until all drug related toxicities have resolved, whichever is later. After 30 days only SAEs considered related to study treatment will continue to be recorded.

### 7.2 Blood Samples for PK evaluations

Blood samples will be collected at pre-dose, 0.5h after dose initiating, EOI, and 0.5h, 4h, 12h, 24h (Day 2), 48h (Day 3), Day 5, Day 8, Day 15, Day 22, and Day 30 post EOI, from all subjects to determine the serum concentration of OsrHSA using a validated immunoassay for PK analyses. Approximately 3 mL blood will be collected at each of the following time points. Serum will be separated and stored for bioanalysis of OsrHSA concentration with a validated assay. The exact/actual time to collect blood will be documented.

An additional blood sample should be collected from subjects experiencing unexpected and/or serious AEs if possible.

The sampling schedules are seen in [Table 1](#).

### 7.3 Immunogenicity Evaluations

Blood samples for ADA analyses will be collected at pre-dose, D8, D15, D22, and D30 post EOI

## **8 DATA COLLECTION AND MANAGEMENT**

Data collection is the responsibility of the clinical trial staff at the site under the supervision of the site investigator. The investigator is responsible for ensuring the accuracy, completeness, legibility, and timeliness of the data reported.

Hardcopies of the study visit worksheets will be used as source document worksheets for recording data for each participant enrolled in the study. Data recorded in the electronic case report form (eCRF) derived from source documents should be consistent with the data recorded on the source documents. All source documents should be completed in a neat, legible manner to ensure accurate interpretation of data.

Clinical data (including adverse events (AEs), concomitant medications, and expected adverse reactions data) and clinical laboratory data will be entered into 21 CFR Part 11-compliant data capture system provided. The data system includes password protection and internal quality checks, such as automatic range checks, to identify data that appear inconsistent, incomplete, or inaccurate. Clinical data will be entered directly from the source documents.

Only individuals who have received training on the EDC are allowed to make eCRF entries, corrections, and alterations. Training must be documented and a log of all EDC users and their rights within the system be maintained. The data management team will raise queries in the EDC system to resolve discrepancies. The Investigator must verify that all data entries in the eCRFs are accurate and correct.

Any outstanding entries must be completed immediately upon notice. No blank sections should be left on CRF and explanations has to be recorded for all missing data. All source documents should be retained. All essential documents should only contain subject coded identifiers and no personal identifying information should be transmitted.

### **8.1 Study Record Retentions**

After completion of the study and when all collected data are validated, the database will be locked, pursuant to the prior approval by the Sponsor (or its designee). Final data will be extracted from the EDC system and delivered in the form of SAS® datasets. A Portable Document Format (PDF) copy of the eCRF will be produced for each study subject and included in the final delivery.

All data obtained during the conduct of the protocol will be kept in secure network drives or in approved alternative sites that comply with sponsors/CROs security standards. Each Subject will have identifiers that will be kept at the study sites.

If clinical site/sponsor becomes aware of loss or destruction of data due to a major breach occurrence that has jeopardized subject confidentiality and trial data, the IRB will be notified.

Study documents should be retained for a minimum of 2 years after the last approval of a marketing application in an ICH region and until there are no pending or contemplated marketing

applications in an ICH region or until at least 2 years have elapsed since the formal discontinuation of clinical development of the study intervention. These documents should be retained for a longer period, however, if required by local regulations. No records will be destroyed without the written consent of the sponsor, if applicable. It is the responsibility of the sponsor to inform the investigator when these documents no longer need to be retained.

## **8.2 Protocol Deviations**

Investigators ascertain they will apply due diligence to avoid protocol deviations. Under no circumstances should the investigator contact the Sponsor if any, monitoring the study to request approval of a protocol deviation, as no authorized deviations are permitted. If the investigator feels a protocol deviation would improve the conduct of the study this must be considered a protocol amendment, and unless such an amendment is agreed upon by the Sponsor and approved by the IRB/IEC/REB it cannot be implemented. All significant protocol deviations will be recorded and reported in the CSR.

It is the responsibility of the site investigator to use continuous vigilance to identify and report, when applicable, deviations within 5 working days of identification of the protocol deviation, or within 5 working days of the scheduled protocol-required activity. All deviations must be addressed in study source documents and if applicable, in eCRFs and study reports, in coordination with the sponsor or their designated CRO. Protocol deviations must be sent to the reviewing IRB per their policies. The site investigator is responsible for knowing and adhering to the requirements of the reviewing IRB.

## **8.3 Publication and Data Sharing**

Both the use of data and the publication policy are detailed within the clinical study agreement. Intellectual property rights (and related matters) generated by the Investigator and others performing the clinical study will be subject to the terms of a clinical study agreement that will be agreed between the Institution and the Sponsor or their designee.

## **9 REGULATORY HUMAN SUBJECT PROTECTION AND REGULATORY OVERSIGHT**

### **9.1 Informed Consent Processes and Documentation**

In obtaining and documenting informed consent, the investigator must comply with applicable regulatory requirements (e.g., 45 CFR Part 46, 21 CFR Part 50, 21 CFR Part 56) and should adhere to ICH GCP. Prior to the beginning of the trial, the investigator should have the IRB's written approval for the protocol and the written ICFs and any other written information to be provided to the participants. Participants will be asked to read and review IRB-approved ICFs and other written information. ICF should include detailed description of study procedures, risk and benefits, directions, participant's rights, compensation if applicable, and contact of Human Subject Protection Services. Additionally, investigator will explain the research study to the participant in terms suited to the participant's comprehension and answer any questions that may arise. Investigator should explain their rights as research participants, study procedures, risk and benefits, anticipated adverse effects. Participants will have the opportunity to carefully review the written consent form and ask questions prior to signing. ICF should be signed prior to any interventions for the study. Participants must be informed that participation is voluntary and that they may withdraw from the study at any time, without prejudice. Participant will be given a copy of the signed consent form and the original consent form will be kept as a permanent record.

### **9.2 Confidentiality and Privacy**

Participant confidentiality and privacy is strictly held in trust by the participating investigators, their staff, and the sponsor(s) and their interventions. This confidentiality is extended to cover testing of biological samples in addition to the clinical information relating to participants. Therefore, the study protocol, documentation, data, and all other information generated will be held in strict confidence. No information concerning the study or the data will be released to any unauthorized third party without prior written approval of the sponsor.

All research activities will be conducted in as private a setting as possible.

The study monitor, other authorized representatives of the sponsor, representatives of the Institutional Review Board (IRB), regulatory agencies or pharmaceutical company supplying study product may inspect all documents and records required to be maintained by the investigator, including but not limited to, medical records (office, clinic, or hospital) and pharmacy records for the participants in this study. The clinical study site will permit access to such records.

The study participant's contact information will be securely stored at each clinical site for internal use during the study. At the end of the study, all records will continue to be kept in a secure location for as long a period as dictated by the reviewing IRB, Institutional policies, or sponsor requirements.

Research data, which is for purposes of statistical analysis and scientific reporting, will be transmitted to and stored at the data management group at the designated CRO. This will not include the participant's contact or identifying information. Rather, individual participants and their research data will be identified by a unique study identification number. The study data entry and study management systems used by clinical sites and by CRO staff will be secured, and password protected. At the end of the study, all study databases will be de-identified and archived at the CRO or Sponsor until further data integration with future studies of OsrHSA.

### **9.3 Conflict of Interest**

The independence of this study from any actual or perceived influence, such as by the pharmaceutical industry, is critical. Therefore, any actual conflict of interest of persons who have a role in the design, conduct, analysis, publication, or any aspect of this trial will be disclosed and managed. Furthermore, persons who have a perceived conflict of interest will be required to have such conflicts managed in a way that is appropriate to their participation in the design and conduct of this trial.

## 10 SAFETY REPORTING

### 10.1 Definition of Adverse Event

An adverse event (AE) is defined as any reaction, side effect, or untoward event that occurs during the course of the clinical trial whether or not the event is considered related to the treatment or clinically significant.

For this clinical trial, AEs will include any events reported by the subject, any new medical conditions, and symptoms, any new abnormal findings on physical examination or laboratory evaluation. Additionally, any worsening of a pre-existing condition or abnormality will also be considered as an AE.

All AEs must be recorded on eCRF. All AEs must be followed return to baseline or stabilizes.

#### Serious adverse events (SAE)

A serious adverse event is defined as any adverse experience that meets any of the following criteria:

- Results in death;
- Is life-threatening
- Requires hospitalization or prolongation of existing hospitalization. Additionally, complications occurring during hospitalization are also considered AEs.
- Results in persistent or significant disability or incapacity (This definition is not intended to include experiences of relatively minor medical significance such as uncomplicated headache, nausea, vomiting, diarrhea, influenza, or accidental trauma (e.g., sprained ankle) which may interfere or prevent everyday life functions but do not constitute a substantial disruption.);

Other important medical events that may not be immediately life-threatening or result in death or hospitalization but, when based on appropriate medical judgment, may jeopardize the subject or may require intervention to prevent one of the outcomes in the definition of SAE listed above should also be considered SAEs. Medical and scientific judgment should be exercised in deciding whether expedited reporting is appropriate in such situations.

The following hospitalizations are not considered to be SAEs because there is no “adverse event” (i.e., there is no untoward medical occurrence) associated with the hospitalization:

- Hospitalizations for respite care
- Planned hospitalizations required by the protocol
- Hospitalization planned before informed consent (where the condition requiring the hospitalization has not changed post study drug administration)
- Hospitalization for administration of study drug or insertion of access for administration of study drug

- Hospitalization for routine maintenance of a device (e.g., battery replacement) that was in place before study entry

